9.1.2 Cytomorphology

Cytologic assessment of all screened and on-study participants will be performed by [name], the designated cytopathologist for this study. She will provide a traditional characterization (QNS, normal, apocrine metaplasia, epithelial hyperplasia, or hyperplasia with atypia) and a semi-quantitative cytology index score (modified Masood score [Masood 1990])

9.2 Serum Assays

Blood will be drawn fasting for adipocytokines and hormones. All baseline and end of study serum assays will be run together along with pooled serum to control for batch variation. Adipocytokines are run using customized Luminex kits in the breast cancer prevention laboratory. Estradiol and testosterone will either be performed in the Breast Cancer Prevention laboratory or, alternatively, at the Ligand Assay and Core Analysis Laboratory at the University of Virginia (UVA). The lower limit of detection for estradiol at the Ligand Lab is 1.5 pg/ml and the intraassay variation is 4.3%. SHBG is assayed by an immunometric assay using the Immulite analyzer (Diagnostic Products Corp), with a lower limit of detection 0.2 nmol/L and intraassay variation of 2.4%.

9.3 Exploratory Molecular Markers

Depending upon funds availability, exploratory studies may be conducted of molecular markers from archived frozen tissue stored at -80°C. This includes RTqPCR for estrogen inducible gene transcripts and a proteomics panel.

If residual cellular material is available, cells may be processed to slides and processed for evaluation of ER expression by immunocytochemistry. ER expression will be assessed with ID5 antibody from Dako diluted at 1:100 and applied for 30 minutes. The ER protocol has been optimized for fine needle aspirate specimens processed as ThinPrep slides [Petroff 2006]. This protocol involves use of low temperature (90°C) retrieval for two minutes with a 0.2X nuclear decloaker (Biocare) and use of a 0.01% glucose oxidase blocking reagent for 30 minutes at 37°C. ER expression will be hand scored by two readers utilizing 100 cells from a hyperplastic duct exhibiting ER staining. The proportion of cells staining at each intensity (0-4+) will be assessed. The proportion of cells staining at each intensity is then multiplied by the intensity to achieve proportion/intensity sub-scores. The weighted intensity score (IS) is computed by adding together the proportion/ intensity sub-scores. Under this system, scores can theoretically range from 0-4. However, for benign hyperplastic cells which average 30% ER expression with 2+ staining, our median intensity score is approximately 0.6.

10. SPECIMEN MANAGEMENT

10.1 Specimen Processing and Laboratories

10.1.1 RPFNA

RPFNA is performed in the Breast Cancer Prevention Center as outlined above. Cytolyt/formalin fixed specimen is placed on a rocker and frozen specimen is kept in liquid nitrogen prior to transport (few hours) and processing in the Breast Cancer Prevention Laboratory. The KUMC Breast Cancer Prevention Center Laboratory, under the direction of [name]. Is located on the first floor of the Cancer Research Building with a total of 1597 square feet plus 400 square feet of office space. The laboratories are fully equipped for cell culture, the processing and assessment of cytology and immunocytochemistry slides, multiple serum and tissue assays (ELISA's RIAs), laser microdissection, RT-qPCR, and various other molecular biology techniques. Staff located in the administrative/laboratory unit include an experienced cytology technician, a masters prepared biologist, and an additional technician experienced in multiple molecular techniques.

10.1.2 Blood Based Assays

Initial processing for blood tests occurs in the Breast Cancer Prevention Center where we have all necessary equipment for phlebotomy, and initial processing including a refrigerated centrifuge and immediate access to a -80°C freezer.

Blood for the chemistry profile will be drawn in a mint gel clot tube performed by a current CLIA certified clinical laboratory. Generally the clinical laboratory at the Cancer Center Clinical Laboratory at the Westwood campus.

Hormones: Two full gel clot tubes are allowed to clot at room temperature for thirty minutes, then spun at 3500 rpm for 15 minutes. 1-1.5 ml aliquots are placed into four polypropylene cryovials. Tubes are then stored in the -80°C freezer until all specimens from a participant can be analyzed in the same batch.

Adipocytokine panel: 1 red serum tube (no gel stopper) is allowed to clot at room temperature for thirty minutes, then centrifuged at 4,100 RPM for 5 minutes at 4°C. Place 1-1.5 ml aliquots into three 2 ml cryovials. Tubes are then stored in the -80°C freezer until all specimens from a participant can be analyzed in the same batch.

Blood for Bazedoxifene Levels: 1 EDTA plasma tube is obtained. Centrifuge at 3000 RPM for 10 minutes. Place 1ml aliquots into two 2 ml cryovials. Tubes are then stored in the -80°C freezer until all specimens from a participant can be analyzed in the same batch.

10.3 Shipping instructions

Samples to be assayed at the University of Virginia will be shipped on dry ice.

11. REPORTING ADVERSE EVENTS

DEFINITION: An adverse event (AE) is any untoward medical occurrence in a study participant. An AE does not necessarily have a causal relationship with the treatment or study participant. An AE can therefore be any unfavorable and unintended sign (including an abnormal laboratory finding), symptom, or disease temporally associated with participation in a study, whether or not related to that participation. This includes any death that may occur while a participant is on a study.

11.1 Adverse Events

11.1.1 Reportable Adverse Events

All adverse events that occur after the informed consent is signed must be recorded on the adverse event CRF whether or not related to study agent.

11.1.2 AE Data Elements

- AE reported date
- AE Verbatim Term
- CTCAE Term (v 4.0)
- Event onset date and event ended date
- Severity grade
- Attribution to study agent (relatedness)
- Whether or not the event was reported as a Serious Adverse Event (SAE)
- Action taken with the study agent
- Outcome of the event
- If participant discontinues trial because of AE
- Comments

11.1.3 Severity of AEs

Identify the adverse event using the NCI Common Terminology Criteria for Adverse Events (CTCAE) version 4.0. The CTCAE provides descriptive terminology and a grading scale for each adverse event listed. A copy of the CTCAE can be found at <http://ctep.cancer.gov>.

AEs will be assessed according to the CTCAE grade associated with the AE term. AEs that do not have a corresponding CTCAE term will be assessed according to their impact on the participant's ability to perform daily activities as follows:

Grade	Severity	Description
1	Mild	Barely noticeable, does not influence functioning Causing no limitations of usual activities
2	Moderate	Makes participant uncomfortable, influences functioning Causing some limitations of usual activities
3	Severe	Severe discomfort, treatment needed Severe and undesirable, causing inability to carry out usual activities

4	Life threatening	Immediate risk of death Life threatening or disabling
5	Fatal	Causes death of the participant

11.1.4 Assessment of relationship of AE to treatment

The possibility that the adverse event is related to study drug will be classified as one of the following: not related, unlikely, possible, probable, definite.

11.1.5 Follow-up of AEs

All AEs, including lab abnormalities that in the opinion of the investigator are clinically significant, will be followed according to good medical practices and documented as such.

11.2 Serious Adverse Events

11.2.1 Definition

ICH Guideline E2A and Fed. Reg. 62, Oct. 7, 1997 define serious adverse events as those events, occurring at any dose, which meet any of the following criteria:

- Results in death
- Is life threatening (*Note: the term life-threatening refers to an event in which the patient was at risk of death at the time of the event; it does not refer to an event which hypothetically might have caused death if it were more severe*).
- Requires inpatient hospitalization or prolongation of existing hospitalization
- Results in persistent or significant disability/incapacity
- Is a congenital abnormality/birth defect
- Events that may not meet these criteria, but which the investigator finds very unusual and/or potentially serious, will also be reported in the same manner.

11.2.2 Reporting Serious Adverse Events to

As per institutional procedures, SAEs will be reported to the University of Kansas Cancer Center Data Safety and Monitoring Committee and to the Human Subjects Committee (KUMC's IRB)

Elements to be reported may include

- Date and time of the SAE
- Date and time of the SAE report
- Name of reporter
- Call back phone number
- Protocol number
- Title of protocol
- Description of the SAE, including attribution to drug and expectedness

All SAE's will be followed until there is resolution or stability based on the PI's judgment.

12. STUDY MONITORING

12.1 Data Management

Investigator/staff will also keep a log of potentially eligible individuals screened for study and if not entered the primary reason they declined participation.

Eligibility checklist and all clinical data capture form (including current medications) will be completed by the PI or clinical staff. Laboratory reports and data will be kept in the participant specific study binders as well. Co-existent disease and adverse events will be coded using the NCI CTCAE, version 4.0.

Source documents will consist of reports (mammogram reports, laboratory reports, etc.), and forms created specifically for this study that will capture information such as physical exam, phone contact information, adverse events, concomitant medications, demographics, etc. Source document files/chart or electronic medical records must be kept available for monitoring and throughout data analysis.

All participants will be registered in the Comprehensive Research Information System (CRIS) managed by the Department of Biostatistics and the Cancer Center's Biostatistics and Informatics Shared Resource. Questionnaires will be completed online by participants for direct entry into REDCAP. Where this is not possible, paper forms will be used and will be directly photocopied (assuring that no personal identifiers such as name or medical record number are retained) and these will be sent for data entry. All data forms will be stored in subject specific binders in the data office. All CRFs and questionnaires will be identified by participant initials and study ID number only. Data from laboratory and other research assessments will be entered into appropriate databases for eventual relay to the biostatistician for merging together with clinical information collected in REDCAP for statistical analyses, including quality control checks.

All data will be audited and verified prior to being considered final. When the database has been declared to be complete and accurate, the database will be locked and sent for statistical analysis.

12.2 Data and Safety Monitoring Committee

This study will be monitored by the University of Kansas Cancer Center Data Safety and Monitoring Committee, as per institutional guidelines. There is a quarterly review of subject recruitment, subject retention, adverse events, and serious adverse events.

12.3 Sponsor Monitoring

Any required clinical monitoring by the provider of the study agent will be accommodated and specific procedures incorporated into the protocol.

12.4 Record Retention

Clinical records for all participants, including CRFs, all source documentation (containing evidence to study eligibility, history and physical findings, laboratory data, results of consultations, etc.), as well as IRB records and other regulatory documentation will be retained

by the Protocol Lead Investigator ([name]) in a secure storage facility in compliance with HIPAA, OHRP, FDA regulations and guidelines.

13. STATISTICAL CONSIDERATIONS

13.1 Study Design/Endpoints

The experimental design for the study is an open label, single arm pilot study of Duavee® as a prevention drug for breast cancer in high risk peri- or post-menopausal women at high risk for development of breast cancer, with Ki-67 positivity of <4%. Participants will receive Duavee® one tablet daily for six months. No randomization or stratification is involved. The primary endpoint is demonstration of feasibility for subsequent trials of Duavee® using a series of pre-set criteria having to do with accrual rate, completion, and lack of evidence for an increase in breast epithelial cell proliferation. A secondary endpoint will examine the specific potential for Duavee® to actually reduce cell proliferation and thus function as a breast cancer chemopreventive agent. A series of exploratory endpoints will document clinical efficacy (relief of vasomotor symptoms) and will examine modulation of other quantitative biomarkers potentially related to breast cancer development.

13.2 Primary Feasibility Endpoints

The primary endpoint overall is an assessment of feasibility that will inform the decision about and the design of subsequent trials. This will be based on considerations of 1) ease of accrual of the target population; 2) acceptance and tolerability of the intervention. Basically, if either fail, then it would indicate that future trials with this approach are not feasible to consider

For the first aspect of accrual, a criterion has been set at 20 participants accrued in 6 months (starting from when the trial is actually open to enrollment). If the accrual rate is slower than this, it would be impractical to conduct a similar trial at a single institution. While total accrual will be used for this initial criterion, the relative ease of accrual into the two cohorts (Cohort A, Ki-67<1%; Cohort B, 1% ≤ Ki-67 < 4%) will be taken into consideration. Certainly it is anticipated that accrual to Cohort A will be easier and faster, but if accrual to Cohort B is not at least half the overall rate (i.e., 20 participants per 12 months) then it would indicate that a trial requiring measurable Ki-67 >1% would not be a feasible option. For this assessment, accrual is considered as meeting all eligibility criteria, signing an informed consent, and receiving the first dose of study agent. This number will then be used for consideration of the second feasibility aspect.

The second aspect of feasibility is retention of participants on trial, completion of the planned 6 months of intervention, and acquisition of repeat RPFNA specimen (plus blood, mammogram, etc.) for assessment of modulation in quantitative biomarkers. A criterion has been set at 85% completion overall. While the ultimate goal is paired samples for comparison of biomarkers (for sample size and power calculation purposes), a high incidence of early problems with participant compliance in general (adverse events, complaints about the study agent or the schedule, etc.) would serve as an indication that the intervention would not be suitable for future trials.

The above criteria are intended to inform consideration of future biomarker trials with Duavee®; not to provide conclusive proof of principle. Thus, pre-set values for “success” or “failure” have been established; rather than a formal approach of statistical analysis and sample size power calculations. The total number of 40 participants represents a reasonable number for a pilot trial. Given our experience with similar biomarker trials using a variety of SERMs or an AI, this size

trial will readily document efficiency in accrual and identify problems with participant acceptance (compliance, retention, completion).

13.3 Primary Quantitative Endpoint

The primary quantitative (but secondary overall) endpoint addresses the specific question that Duavee® might produce the deleterious effect of increasing breast cell proliferation. While there is no evidence for this (and the FDA does not consider this a risk to be included in labelling) it is still a perceptual concern by women and providers. Thus, an assessment will be made of the frequency of participants that exhibit a likely clinically meaningful increase in Ki-67. This will be defined differently for the two cohorts, but both will contribute to the analysis of potential increase. For Cohort A (initial Ki-67 < 1%), a meaningful increase is defined as any value of 2% or greater on the off-study aspiration. For Cohort B (initial Ki-67 \geq 1% but <4%), a meaningful increase is defined as a doubling or greater of the initial rate (i.e., a repeat aspiration value of at least 2%). Historically, for women in our High Risk Breast Clinic similar to those being enrolled in this study, approximately an 11% incidence of Ki-67 increasing is observed in the absence of any intervention. Therefore, with a minimum (per feasibility endpoint #2) of 34 paired specimens in which to assess change, an observed frequency of 10% or less would provide assurance that the true rate does not exceed 20% (95% confidence interval). Conversely, an observed frequency as high as 20% could still accommodate a true rate of 10%. Thus, as long as the observed frequency is \leq 20%, subsequent trials could be designed with a placebo-control arm. Only for an observed frequency >20% would it be impractical to design future biomarker trials.

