1.1 Primary Feasibility Objective

To determine feasibility for a larger clinical trial in women at moderately increased risk we will:

1.1.1 Determine if accrual is brisk as demonstrated by accrual of at least 20 moderate risk women in the initial 6 months (3.5 entrants per month) in a single institution;

1.1.2 Determine if there is a 15% or lower dropout rate over the 6 month intervention; and

1.1.3 Determine if 20% or fewer women with paired RPFNA specimens exhibit a meaningful increase in benign breast cell proliferation (Ki-67) where meaningful increase is defined as an increase in Ki-67 to 2% or higher in individuals with initial Ki-67 < 1% or a doubling of Ki-67 in individuals with initial Ki-67 of 1% or higher.

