8. CRITERIA FOR EVALUATION AND ENDPOINT DEFINITION

8.1 Primary Endpoint

Prior to formal analysis, there are two aspects of a feasibility trial that are based on simple numbers. If we cannot accrue 40 eligible women within a reasonable time (no more than 12 months) and/or if more than 15% of enrolled participants do not complete the study, then it would not be practical to propose future studies.

For the Specific Aim of documenting that Duavee® does not cause a meaningful increase in proliferation, only participants for whom paired specimens evaluable for Ki-67 will be included. An increase in Ki-67 will be defined by one of two scenarios: a) from a baseline Ki-67 <1% to a Ki-67 >2%; or b) for a baseline Ki-67 >1%, at least a doubling of the baseline value.

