13.4 Secondary Exploratory Endpoints

This study is not specifically powered to address the objectives of estimating favorable change in quantitative biomarker endpoints that may be related to risk for development of breast cancer.

The most critical biomarker from a breast cancer prevention standpoint is that of cell proliferation, specifically a reduction in value for participants whose baseline specimen exhibited sufficient Ki-67 staining (1% that there is the potential for a decrease). Thus, this analysis will be limited to those participants in Cohort B. Also this parameter will be analyzed first and separately from all other biomarkers. Descriptive statistics will be used to summarize the values of Ki-67 (percent of cells staining positive) in the baseline specimen, the 6-month (off-study) specimen, and the change (both absolute and relative) from baseline to off-study. For statistical analysis, the Wilcoxon signed-rank test will be used to accommodate the expected small sample size and to avoid any assumptions regarding normal distributions. Only participants who provide paired specimens evaluable for Ki-67 will be included in this analysis. However, for off-study specimens where the cell yield is so low (<100 cells per slide) that assessment of Ki-67 is not even possible, an anti-proliferative effect can be inferred. Thus, a value of 0.5% will be imputed as a reasonable compromise between imputing a value of 0% (no evidence of any proliferation) and a value of 1% (e.g., only 1 positive cell out of 100 counted). Since a non-parametric approach is used, the exact imputed value has minimal impact given that the criterion for inclusion is a baseline value of 1%. For this primary evaluation of modulation of a quantitative measure, $p < 0.05$ will be considered the criterion for statistical significance.

Should there be adequate, paired specimens, further exploration of this primary endpoint variable, relative change in Ki-67, will be accomplished by developing an appropriate model and testing covariates. If necessary, an appropriate transformation will be used in this regression.

For these possible analyses, as for the exploratory analyses below, no adjustment will be made for multiple comparisons, but the results will be interpreted with caution.

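### The pooled 20% Ki-67 rule turns on a cohort mix that the plan does not fix, and no named analysis would show a rise in Cohort A that stays below 2%

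*Combined protocol and SAP*

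**What the plan says.** Section 1.1.3 sets the objective that "20% or fewer women with paired RPFNA specimens exhibit a meaningful increase in benign breast cell proliferation". It defines the event as "an increase in Ki-67 to 2% or higher in individuals with initial Ki-67 < 1% or a doubling of Ki-67" where the initial value is 1% or higher. Section 13.3 repeats this by cohort. For Cohort A, "a meaningful increase is defined as any value of 2% or greater on the off-study aspiration"; for Cohort B the value must at least double. On pooling it says "This will be defined differently for the two cohorts, but both will contribute to the analysis of potential increase". The decision rule is "Only for an observed frequency >20% would it be impractical to design future biomarker trials".

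On the mix, section 13.2 says "Certainly it is anticipated that accrual to Cohort A will be easier and faster". It gives no expected split, quota or cap. It does set a benchmark that Cohort B should accrue at half the overall rate or better, but that benchmark judges whether a later trial requiring measurable Ki-67 is feasible.

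The descriptive statistics and signed-rank test for Ki-67 are in section 13.4: "Thus, this analysis will be limited to those participants in Cohort B". Section 8.2 has the same restriction. Ki-67 is not in the section 13.4 list of variables to be assessed in all paired participants.

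**The concern.** The two event definitions treat the same proportional change differently. A move from 0.4% to 1.8% is no increase, while 1.0% to 2.0% is one. Cohort A women always enter the denominator, but under a moderate rise they seldom enter the numerator. The more Cohort A women enrolled, the easier the rule is to pass, whatever the drug does.

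The overall purpose in section 1 is to show, in a preliminary way, that proliferation does not increase, and the absence of a significant Ki-67 increase is one condition for a larger trial. A rise confined below 2% in Cohort A would be recorded in the data but would appear in no named analysis.

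**Working it through.** **Inputs from the plan.** 40 enrolled; 85% completion (13.2); 34 pairs, a 20% mark and about 11% untreated increases (13.3); 500 cells scored (9.1.1), so 1% is 5 cells and 2% is 10 cells.

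**Assumptions of mine.** A drug that doubles Ki-67 in every woman; the cohort mix; the distribution of baseline Ki-67; the variation within a woman between aspirations. The plan gives none of these.

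**1. The plan's own figure.** 0.85 × 40 = 34. The normal-approximation interval at 10% is 0.10 ± 1.96 × √(0.10 × 0.90 / 34), or -0.1% to 20.1%, which reproduces the stated 20%. At 20% it is 6.6% to 33.4%, which contains 10%, as the plan says.

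**2. The rule as a count.** 0.20 × 34 = 6.8, so the rule passes with 6 or fewer events. It passes more often than not when the true pooled event rate is below 19.4%.

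**3. Exact doubling.** If baseline b < 1%, then 2b < 2%, so Cohort A yields no events and Cohort B yields all of its women. With Cohort A share a, P(pass) = P(Binomial(34, 1 − a) ≤ 6).

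**4. Adding 500-cell counting error.** P(at least 10 of 500) is 0.8% when a true 0.4% doubles to 0.8%, 8% when it triples to 1.2%, and 28% when 0.8% doubles to 1.6%. Over the assumed baselines, a doubling gives an event probability of about 0.53 in Cohort B and 0.03 to 0.13 in Cohort A. The pooled rate is a × pA + (1 − a) × pB. At a = 0.80 that is 0.80 × 0.03 + 0.20 × 0.53 = 0.13, up to 0.80 × 0.13 + 0.20 × 0.53 = 0.21.

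**5. Adding within-woman variation.** A lognormal model was tuned, at each mix, as near as it would go to the plan's 11% untreated rate.

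P(pass) under a universal doubling, 34 pairs (column 3 uses unrounded probabilities):

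| Cohort A share | Exact doubling | With counting error | Lognormal, tuned towards 11% untreated |
|---|---|---|---|
| 60% | 0.5% | 10-29% | 6-7% |
| 70% | 8% | 23-57% | 21-22% |
| 75% | 22% | not run | 32-35% |
| 80% | 47% | 43-84% | 39-50% |
| 85% | 76% | not run | 71% (untreated only 8-9%) |
| 90% | 95% | 67-98% | 94% (untreated only 5%) |

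At 50% Cohort A, counting error gives 4-12%. If every Cohort A baseline were zero, the figure at 50-60% could reach about 40%.

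**6. A second model.** Gamma-distributed Ki-67 with within-woman CV from 0 to 0.8 gives about 95% or more passing at 87% Cohort A, 61-83% at 76-81%, and 32-61% at 70-75%. The settings with the highest pass rates have untreated event rates of roughly 0.2-7%, below the plan's 11%. Gamma settings near 11% pass 12-28%.

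**7. What an all-pairs analysis would see.** In the gamma simulations a signed-rank test on all 34 pairs detects the doubling in 72-99% of trials. Its upward false-positive rate is 2-9% against a nominal 2.5%. Tested alone, Cohort A gives 13-49% false upward results, because it was selected on low readings.

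**The case against.** The 2% threshold is deliberate. Section 2.3 ties a labelling index of 2% or higher to increased breast cancer risk, and in both cohorts an event ends at 2% or above. A change from 0.4% to 0.8% is 2 versus 4 cells in 500, and not counting it in one woman is sensible. This stands, and it is why the definition should stay.

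A reader might infer that a doubling would usually pass whenever Cohort A is in the majority. The documents and the arithmetic do not support that. At 50-60% Cohort A the rule usually flags the drug, and the highest pass rates come from settings below the plan's background rate. A heavy Cohort A share is also not established. Section 2.3 puts normal postmenopausal Ki-67 at 0-1%, but it also reports a median of 1.4% in high-risk postmenopausal aspirates with hyperplasia, and section 9.1.1 scores the ducts that stain most. The same section warns that values of 1-2% may be hard to find in definitively postmenopausal women and says that the peri-menopausal proportion has not been adequately studied. The mix is simply unknown.

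A reader might also infer that Cohort A is ignored outright. It is not: its rises to 2% count. Section 13.5 admits all paired participants to the biomarker analyses, and section 13.4 allows modelling of relative Ki-67 change. Neither names Cohort A, however, and relative change is undefined at a baseline of zero.

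Finally, section 13.2 disclaims conclusive proof for the feasibility criteria, and a pass in 13.3 means only that a placebo-controlled trial could be designed. That limits the stakes but does not remove the gap.

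**Conclusion.** The point holds in conditional form. The asymmetric definition, the pooling and the lack of a named analysis of Ki-67 change that includes Cohort A are all in the text. Under a universal doubling with 34 pairs and 500 cells, the rule passes about half the time or more when Cohort A is roughly 75-80% or more of pairs: about 40-85% at 76-81%, and about 95% or more at 87%, the latter at an untreated rate below 11%. With counting error alone, the halfway point ranges from about 65% to 85% Cohort A, depending on how low the baselines lie.

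Where the model matches the 11% background, the pass rate follows the mix: 12-28% in the gamma settings, and from 6-7% at 60% Cohort A to 39-50% at 80% in the lognormal model. Section 13.3 does not say how the historical 11% was defined, so that calibration is itself approximate. All of this rests on assumed baseline distributions and within-woman variation.

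The plan should be changed because the remedy costs little and bears on the stated purpose. Failure of the rule is not the expected outcome.

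**What to change.** Keep the 2%/doubling definition and keep 20% as the go/no-go mark. In section 13.3 add:

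- One supporting analysis on all evaluable pairs, Cohorts A and B together: absolute paired change in Ki-67 (off-study minus baseline), with a Hodges-Lehmann estimate and 95% CI. Read it beside the 20% result before concluding that Duavee does not increase proliferation. Attach no formal pass/fail gate, since no margin has been set.
- The frequency of meaningful increase by cohort, with exact CIs, beside the pooled figure.
- A description of Ki-67 change in Cohort A, without a separate test.
- Counted specimens only. The 0.5% value that section 13.4 imputes for low-yield specimens is justified there by a baseline of at least 1%. In Cohort A it could turn a baseline of 0-0.4% into a spurious rise.

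While editing, reconcile the event wording: section 8.1 has "from a baseline Ki-67 <1% to a Ki-67 >2" per cent and a baseline above 1% for the doubling rule, which leaves exactly 1% unclassified. Sections 1.1.3 and 13.3 use 2% or higher and 1% or higher.

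The cost is a few lines of text and one analysis of data already collected. State one drawback: the below-4% entry cap and the lack of a control arm give the all-pairs estimate a slight upward drift, seen above as the 2-9% false-positive rate.
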